### B1. PURPOSE OF PROTOCOL

The purpose of the protocol is to test the hypothesis that elimination of the use of non-depolarizing neuromuscular blocking agents (NMBA) for maintenance of general anesthesia in patients at high risk of developing postoperative pulmonary complications (PPCs) undergoing non-cardiac operations is associated with reduced risk of PPCs.

*Specific Aim 1:* To test the primary hypothesis that avoidance of non-depolarizing NMBAs, as compared to standard care which includes the use of non-depolarizing NMBAs, is associated with a lower risk of a composite of PPCs (including respiratory failure, suspected respiratory infection, aspiration pneumonia or pneumonitis, atelectasis, bronchospasm and reintubation within 28 days of index operative procedure) and all cause in-hospital mortality both within 28 days of index operative procedure.

*Specific Aim 2:* To test the key-secondary hypothesis that avoidance of non-depolarizing NMBA, compared to standard care which includes the use of non-depolarizing NMBA, is associated with higher vasopressor equivalent dose, which may be the consequence of higher dosing of opioids and anesthetics. Further, we shall also evaluate the following secondary endpoints: duration of intraoperative hypotension (defined as mean arterial pressure <55mmHg), surgeon's assessment of surgical field, cost of anesthetic medications, time to PACU discharge readiness (interval between arrival and time when meeting PACU discharge criteria), rate of unplanned ICU admissions or return to operating room within 24 hours, hospital length of stay and 30-day readmission rates.

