### B3. DESCRIPTION OF RESEARCH PROTOCOL

#### A. STUDY DESIGN – OVERVIEW, METHODS, PROCEDURES

##### Experimental design and methods

**Study Design**

Pragmatic prospective randomized controlled assessor-blinded effect-size finding trial at two academic tertiary care hospitals: Beth Israel Deaconess Medical Center (BIDMC) and Massachusetts General Hospital (MGH).

Prior to randomization, if subjects are eligible on the basis of inclusion and exclusion criteria, informed consent will be obtained from the participants. Once informed consent is obtained, patients will be randomized in a 1:1-ratio to one of two study arms: standard care non-depolarizing NMBA use (**C**) versus avoidance of non-depolarizing NMBA (**NR**) by computer-generated variable block size random allocation stratified a) study site (MGH or BIDMC) and b) expected preoperative risk of PPC (<40% and ≥40%) as predicted by expanded risk stratification tool as defined above (**Table 1**). Since blinding to use of NMBA is unfeasible, anesthesia team members would be aware of group assignment.

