### Study Endpoints:

1. Primary Endpoint: Composite of postoperative pulmonary complications (respiratory failure, suspected respiratory infection, aspiration pneumonia or pneumonitis, atelectasis, bronchospasm and reintubation) and all cause in-hospital mortality both within 28 days of index operative procedure
2. Secondary endpoint (safety):
  - a. Vasopressor use between groups,
  - b. Duration of intraoperative hypotension (defined as mean arterial pressure <55mmHg),
  - c. Surgeon's assessment of surgical field.
3. Other end points:
  - a. Time to post-anesthesia care unit (PACU) discharge readiness,
  - b. Cost of anesthetic medication,
  - c. Rate of unplanned ICU admission or return to operating room within 24 hours,
  - d. Hospital length of stay
  - e. 30-day readmission rates.

The following baseline variables will also be collected: Clinical and demographic variables will be collected including age, gender, body mass index, type and severity of chronic lung disease, ASA class, obstructive sleep apnea, use of CPAP/Bipap, smoking history, hypertension, coronary artery disease, heart failure, cerebrovascular accident or neurologic dysfunction, history of aspiration, use of home oxygen, chronic kidney disease, diabetes mellitus, Charlson comorbidity index and Procedural Severity Score. Additionally, to track other important intraoperative and postoperative

factors related to overall patient outcome and protocol adherence, we will record administrative, demographic, clinical and billing data including:

- Vital Signs
- Medications administered
- Ventilator settings
- Urine output
- End tidal carbon dioxide concentration
- Dead space ventilation
- Alveolar-Arterial oxygen gradient
- Blood transfusion history
- Length of operation
- Type of operation

*Assessment of Primary Outcome:*

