## 1. STATISTICAL CONSIDERATIONS

- a. **Sample Size Justification:** Assuming the incidence of PPC to be 40% and 15% in Groups C and NR, respectively, we estimated that we would need at least 50 patients in each group to achieve a two-sided  $\alpha = 0.05$  and 80% power. Although the effect size in this assumption is high, if a difference of this magnitude is observed, the study will be well-powered. However, due to the scant knowledge about the directionality of the effect that we are exploring, observing even a smaller difference in this preliminary study will be useful in estimating a reliable effect size that can be used in designing a larger, more definitive study in the future. Results from our secondary endpoints will provide valuable exploratory data on the safety and efficacy of maintenance of general anesthesia without non-depolarizing NMBA.
- b. **Data Analysis:** Descriptive statistics will be assessed and presented as mean( $\pm$ -SD), median(IQR) or frequencies and proportion depending on type and distribution. Differences between groups in continuous variables will be compared using parametric or non-parametric tests as appropriate. Categorical data including the primary outcome (composite of PPC and all cause 28 day in-hospital mortality) will be compared with Chi-square or Fisher's exact test as appropriate. Two-sided p-value of less than 0.05 will be considered significant for all analyses. Logistic regression will be used to assess the relationship between the composite outcome and use or avoidance of non-depolarizing NMBA. Data will be presented as odds ratio and 95% confidence intervals. Individual outcomes will be reported to demonstrate potential trends between the two groups. Continuous outcome variables will be compared between treatment groups using t-test or Wilcoxon rank sum test as appropriate. Exploratory sensitivity analyses will be conducted to analyze if treatment effects were moderated by study site, surgical site or preoperative risk score after adjusting for patient and procedural risk factors such as Charlson comorbidity index and Procedural Severity Score. Statistical consultation shall be provided by [name], PhD at MGH. Statisticians will be blinded to group assignment.

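### The plan applies one unadjusted 0.05 threshold to every analysis, which contradicts its own exploratory labels and leaves its endpoint tiers without a testing order

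*Combined protocol and SAP*

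**What the plan says.** The threshold is in section 1, Statistical Considerations, under b. Data Analysis: "Two-sided p-value of less than 0.05 will be considered significant for all analyses". It carries no exception.

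The text around it points the other way. Under a. Sample Size Justification the plan says "Results from our secondary endpoints will provide valuable exploratory data". Data Analysis says the individual outcomes are there to show possible trends, and it labels the analyses of moderation by study site, surgical site and preoperative risk score as exploratory.

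The endpoint tiers are set out twice, and differently:

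- **B1, Specific Aim 2** gives one key-secondary hypothesis to be tested, that avoiding the agents "is associated with higher vasopressor equivalent dose". It lists seven further secondary endpoints.
- **Study Endpoints** marks no key secondary. Its first secondary item reads "Vasopressor use between groups". It keeps three endpoints as secondary (safety) and puts the other five under a separate heading for other endpoints.

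No section gives a multiplicity adjustment, a testing order or an allocation of alpha.

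**The concern.** This is a stated decision rule, not a missing detail, and it conflicts with the labels beside it. An analyst who follows the threshold sentence would call an exploratory p-value of 0.04 significant. An analyst who follows the labels would not. The plan does not say which governs.

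The key secondary is the most exposed. Aim 2 says it will be tested, the sample-size paragraph calls secondary results exploratory, and the endpoint list names it differently. An equivalent dose is a continuous quantity, for which the plan offers a t-test or Wilcoxon test. Vasopressor use could also be read as yes or no, which would lead to a Chi-square or Fisher test.

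The results are meant to be used. Section B2 (Significance) expects them to inform practitioners' decisions as well as supply pilot data, and B5 expects them to inform choices about these agents. A chance difference in readmission, cost or length of stay that is reported as significant could be carried into either use.

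**Working it through.** **Inputs.** The threshold is two-sided 0.05 (Data Analysis). Study Endpoints lists 3 secondary and 5 other endpoints, so 3 + 5 = 8 non-primary endpoints; Aim 2 gives the same eight as 1 + 7. There is one primary composite. Its parts are "respiratory failure, suspected respiratory infection, aspiration pneumonia or pneumonitis, atelectasis, bronchospasm and reintubation) and all cause in-hospital mortality", which makes 6 + 1 = 7 components. There are 3 moderators. The documents give no correlations between endpoints, so those below are assumptions.

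**1. The plan's own figure.** The plan states no family-wise error rate. Its one checkable number is the sample size: "Assuming the incidence of PPC to be 40% and 15% in Groups C and NR, respectively", two-sided 0.05, 80% power, 1:1 allocation, giving "we would need at least 50 patients in each group". With pooled variance under the null and mean rate (0.40 + 0.15)/2 = 0.275:

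n = [1.960 × √(2 × 0.275 × 0.725) + 0.842 × √(0.40 × 0.60 + 0.15 × 0.85)]² / 0.25² = 48.9, so 49 per arm.

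This reproduces the stated 50 to within one patient. Power at 50 per arm is 80.9%. The calculation spends the full 0.05 on one primary test.

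**2. Chance of at least one declared significance among k true nulls.** For independent tests this is 1 − 0.95^k. The correlated figures come from simulating equally correlated two-sided z-tests (200,000 runs).

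| Tests counted | Independent | ρ = 0.3 | ρ = 0.5 | ρ = 0.7 |
|---|---|---|---|---|
| 8 non-primary endpoints | 33.7% | 29.9% | 25.0% | 19.1% |
| 9 endpoints, with the primary | 37.0% | 32.5% | 26.8% | 20.2% |
| 19 tests (9 + 7 components + 3 moderators) | 62.3% | 52.5% | 40.9% | 28.4% |

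The first row is the relevant one. The last row is an outer bound: it treats each component and each moderator as one formal test, and the plan names no separate tests for the components. With independent tests, 14 are needed before the chance passes 50%.

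**3. The primary test.** It is a single test at 0.05. Its type I error does not depend on what is done with the other endpoints.

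**4. Possible remedies.**

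- Primary and key secondary each at 0.05 with no order: 1 − 0.95² = 9.75% if both are null and independent.
- Key secondary tested only after a significant primary: at most 5% for the pair. If the primary is null, a false claim needs a false-positive primary first. If only the key secondary is null, its own test is at 0.05.
- Bonferroni over 9 endpoints (0.05/9 = 0.0056 each): primary power at 50 per arm falls from 80.9% to 51%, or 82 per arm would be needed.

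**The case against.** The strongest reply is that this is a preliminary, effect-size-finding trial of about 100 patients. It has one primary endpoint and openly labels the rest exploratory, and unadjusted p-values are common for such endpoints. Nothing in the documents says that a secondary result on readmission, cost or length of stay would be treated as established. Much of this stands, and it limits the point to a conflict over what may be called significant. It does not remove the conflict, because the threshold sentence makes no exception for the analyses labelled exploratory.

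The eight-null scenario can also be challenged. Aim 2 expects a real rise in vasopressor dose. Leaving that endpoint out gives 1 − 0.95^7 = 30% with independent tests, and less with correlation. Correlation is plausible for vasopressor use with hypotension and for ICU admission with length of stay, so 34% is the upper end.

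Three stronger readings might be inferred and are not supported:

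- **A false positive is more likely than not.** The eight endpoints give at most 34%, and all nine at most 37%. Passing 50% requires counting components and possibly moderators as formal tests with low correlation.
- **The plan does not separate its endpoints at all.** It does: Aim 2 names a key secondary, Study Endpoints has tiers, and Data Analysis labels components and moderators. What is missing is the link from those tiers to the threshold.
- **The primary conclusion is inflated.** It is not.

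The difference between vasopressor use and vasopressor equivalent dose is a matter of endpoint definition. It needs correcting alongside, but it adds nothing to the error rates above.

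**Conclusion.** The concern holds in a limited form. The blanket threshold contradicts the exploratory and trend labels in the same section, and no order or allocation connects the tiers to it. If all eight non-primary endpoints are null, the chance that at least one is declared significant is about 34% if independent and about 19% to 30% at assumed equal correlations of 0.7 down to 0.3.

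The primary's 5% assumes that one test decides. The plan names both a Chi-square or Fisher comparison and a logistic regression without saying which governs. The two are highly correlated, so any inflation from that is slight.

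The point should be settled before analysis because it determines what the report may declare. It does not threaten the primary result, the sample size or the design.

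**What to change.** Replace the threshold sentence in Data Analysis with:

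> Two-sided p<0.05 is the significance threshold for the primary composite. The key secondary, vasopressor equivalent dose, is tested at 0.05 only if the primary is significant, and otherwise is reported as exploratory. All other endpoints, individual components and moderator analyses are exploratory and are reported as estimates with 95% CIs, without a claim of significance.

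Use the same tiers and the term vasopressor equivalent dose in both Specific Aim 2 and Study Endpoints.

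The sample size and the 80.9% primary power at 50 per arm are unchanged, and no Bonferroni adjustment is needed. There are two costs. Fewer secondary results can be called significant, including the hypotension and surgical-field safety endpoints, although their estimates and intervals are still reported. The key secondary loses its formal test whenever the primary is not significant, which has a probability of about 19% (100 − 80.9) even under the planned 40% versus 15%, and more if the true effect is smaller.

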### **Preliminary studies**

Our study is aimed at patients with high pre-test probability of developing PPCs. In order to identify such patients preoperatively we developed a risk prediction score (**Table 1**) using data from all patients who underwent non-cardiac procedures under general anesthesia with endotracheal intubation at MGH and BIDMC between 2007-2015. 12.2% patients developed PPC (defined as a composite of reintubation within 7 days and respiratory failure, respiratory infection, bronchospasm, atelectasis, pleural effusion, aspiration pneumonitis, pneumothorax within 28 days). Our risk prediction-model which we developed using our published standards demonstrates good discrimination (AUROC of 0.84). We plan to use this prediction instrument along with expanded definition of high risk surgical services as defined by well validated SPORC score (vascular,

transplant, neurosurgery, thoracic, general and burn surgery) and physician review of electronic health records to determine “high risk surgery” to screen for eligibility. **Table 2** shows the predicted incidence of PPC in different risk subgroups of patients (MGH and BIDMC) in an 18-month period.

Risk Prediction Score		Estimated Risk of outcome	
High-risk surgery*	13	Score Point Value	Probability of Outcome (%)
Inpatient surgery	11		
Pneumonia within 1 month	8	0	0.2
ASA $\geq 3$	3	5	0.9
Age $\geq 80$	2	10	3.5
Duration of surgery > 3 hours	2	15	12.3
History of heart failure within 1 year	2	20	35.4
Alcohol abuse within 1 year	1	25	68.2
Home oxygen therapy	1	30	89.3
BMI < 18.5 kg/m 	1	35	97.0
Chronic pulmonary disease within 1 year	1	40	99.2
Total points	44	44	99.8
*ENT, thoracic, vascular, transplant, neurosurgery, thoracic, general, and burn surgery			

\*The expanded definition of high risk surgical services as defined by SPORC score includes vascular, transplant, neurosurgery, thoracic, general and burn surgery.

**Table 1:** Risk prediction tool and estimated risk of outcomes. Logistic regression was used to build a model including all candidate predictors. Stepwise elimination was performed with a  $p = 0.01$  for retaining in the model. Individual weighting values were determined by dividing the respective beta coefficient by the overall smallest beta coefficient of all predictor variables. Rounded to the nearest integer, the score point values were multiplied by the corresponding predictors, thus estimating the final prediction instrument.

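### Vasopressor dose (the key secondary) and minutes of hypotension are compared without covariate adjustment: the tests are valid, but some precision that baseline data could recover is lost, and the vasopressor metric is not defined as a total or a rate

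*Combined protocol and SAP*

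**What the plan says.** Specific Aim 2 in B1 sets the key secondary hypothesis: avoiding non-depolarizing agents is "associated with higher vasopressor equivalent dose, which may be the consequence of higher dosing of opioids and anesthetics". The Study Endpoints section lists vasopressor use as a safety secondary without saying how it is measured. It also lists "Duration of intraoperative hypotension (defined as mean arterial pressure <55mmHg" and a surgeon rating. Neither vasopressor dose nor time in hypotension is divided by length of case.

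Section 1.b gives one rule for such outcomes: "Continuous outcome variables will be compared between treatment groups using t-test or Wilcoxon rank sum test as appropriate". On significance it adds: "Two-sided p-value of less than 0.05 will be considered significant for all analyses". The only adjustment of treatment comparisons for patient or procedural risk is in exploratory analyses of effect moderation (by study site, surgical site and risk score), which give the Charlson index and the Procedural Severity Score as example covariates. They are not tied to these two endpoints and do not name case length.

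On design, "patients will be randomized in a 1:1-ratio to one of two study arms", stratified by site and by predicted PPC risk (below 40% versus 40% or more). The risk score in Table 1 (Preliminary studies) includes surgical service and the item "Duration of surgery > 3 hours". Actual length and type of operation are recorded, with no stated role in the main comparison.

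**The concern.** A patient in a long vascular operation has more time in which to become hypotensive and to receive vasopressor than a patient in a short one, whichever arm they are in. With an unadjusted test, that spread counts as noise. Part of it can be predicted from information available before randomisation.

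Aim 2 is the trial's named key secondary and a safety question, and the protocol itself expects harm in the no-relaxant arm. The trial is also meant to supply effect sizes for a larger study. An interval wider than necessary makes a null safety result easier to misread as reassurance, and makes the estimate less useful for planning.

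**Working it through.** **1. The plan's own sample size.** Inputs from Section 1.a: "Assuming the incidence of PPC to be 40% and 15% in Groups C and NR, respectively", two-sided alpha 0.05, 80% power. With pooled p = (0.40 + 0.15)/2 = 0.275:

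n = [1.96·√(2·0.275·0.725) + 0.842·√(0.40·0.60 + 0.15·0.85)]² / 0.25² = 48.9, so 49 per arm.

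The plan says "we would need at least 50 patients in each group", so its figure reproduces. It covers the binary primary only. No SD, effect size or power is given for any continuous endpoint.

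**2. Does stratification already absorb the variation?** Table 1 gives 35.4% at score 20 and 68.2% at score 25.
- The logits are −0.60 and 0.76, a slope of about 0.273 per point.
- Interpolated risk is 41.9% at score 21 and 62.0% at score 24.
- Entry requires a score of at least 20, so by the score alone only a score of exactly 20 falls below 40%.
- High-risk surgery (13) plus inpatient surgery (11) is already 24, and outpatients are excluded. Every high-risk-service patient is therefore in the upper stratum, whatever the service and whether or not the case exceeds 3 hours (2 points).

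The risk stratum separates almost nothing by case length or type of surgery.

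**3. Analytic size of the loss.** Let R² be the share of outcome variance explained by baseline covariates. The documents give no R², so a range is shown. At 50 per arm and an assumed difference of 0.5 SD, the noncentrality is (0.5/√(1−R²))·√(50/2), with 98 df. The unadjusted sample size giving the same precision is 50/(1−R²).

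| Assumed R² | Power | Unadjusted n per arm for the same precision |
|---|---|---|
| 0 | 69.7% | 50 |
| 0.1 | 74.2% | 56 |
| 0.2 | 79.0% | 63 |
| 0.3 | 84.1% | 72 |

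**4. Simulation with skew and zeros.** All inputs are assumed:
- 100 patients, with planned duration lognormal (median 3.2 h, log-SD 0.5)
- actual duration = planned × lognormal noise (log-SD 0.25)
- six services (log-SD 0.4)
- dose rate with log-SD 0.6 or 0.9, and outcome a whole-case total.

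The adjusted test regresses ranks on arm, site, duration and three service groups.

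| Effect (log scale) | Rate log-SD | Zeros | Wilcoxon | Adjusted, over-3-hour flag | Adjusted, planned minutes |
|---|---|---|---|---|---|
| 0.5 | 0.6 | 15% | 48–49% | 53–54% | 55% |
| 0.6 | 0.6 | 15% | 62–63% | 68% | 71% |
| 0.5 | 0.9 | 15% | 34% | 34–35% | not shown |
| 0.5 | 0.6 | none | 77% | 87% | 91% |

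Ranges reflect repeated runs of 3,000 to 4,000. Type I error was close to 5%. The PPC-risk stratum was not in these models.

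A second simulation used lognormal totals, a true ratio of 1.5, and a rank model on continuous planned length. Gains over Wilcoxon ran from about 2 points (30% to 32%, with 20% zeros) to 24 points (71% to 95%, no zeros).

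**The case against.** Much of the opposing case stands.

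- **Nothing is invalid.** A reader might infer that the unadjusted test biases the safety comparison. It does not: randomisation protects it, and only precision is lost. The plan claims no power for this endpoint, calls secondary results exploratory and describes the trial as a pilot.
- **The metric is undefined.** A reader might take vasopressor dose to be a whole-case total. That is the natural reading, but neither Aim 2 nor the endpoint list says so. If it were a rate, the case-length argument would weaken for this endpoint, though type of surgery would still matter. Hypotension minutes are unaffected.
- **The rise from 70% to 84% is not an expected gain.** It needs an R² of 0.3, for which the documents offer no support, and they give no distribution of case length.
- **Planned length is only partly available.** Scheduled minutes are not listed as collected. The over-3-hour item belongs to the eligibility score, but Table 1 does not say it means planned duration, and high-risk-service patients reach 20 points without it.
- **The plain t-test is a competitor.** With 15% zeros and rate log-SD 0.6 it gave 51.9% and 66.1% (effects 0.5 and 0.6), about 2 points below the flag-adjusted rank model. With 20% zeros in the second simulation it was close to or above the rank model.
- **The exploratory analyses touch the issue** through surgical site and the Procedural Severity Score. They are not the main comparison for these endpoints.

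What remains is that the main analysis of the key secondary ignores baseline information already in the eligibility score, and using it costs almost nothing.

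**Conclusion.** The point holds as a modest, inexpensive gain in precision together with a gap in definition. The planned tests are valid. They leave variation from type of surgery, and from case length where the outcome accumulates, in the error, and stratification does little to remove it.

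The size cannot be derived from the documents. With the information most likely to be on file (over-3-hour flag and three service groups), the gain under assumed inputs is about 0 to 6 points of power with 15% zeros and about 10 with none. It is larger if planned minutes are recorded, and near zero when dosing is noisy. The stratification argument rests on interpolating Table 1 and on strata following the score, although eligibility also involves physician review.

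The documents do not support a claim of bias, of a failed power statement, or of any particular R². Priority is low to moderate.

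**What to change.** In Section 1.b:

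1. State whether vasopressor equivalent dose is a whole-case total or a rate (per hour, per kg), and use the same definition in B1 and Study Endpoints.
2. For this endpoint and for minutes with MAP below 55 mmHg, make the main comparison a pre-specified model with terms for arm, site, PPC-risk stratum, the over-3-hour item as fixed at screening (scheduled minutes if recorded), and surgical service in two or three groups fixed in advance. Say that the risk-stratum term is dropped if one stratum is empty or nearly so.
3. Take the p-value from the adjusted rank model. A difference in ranks has no clinical unit, so also report an adjusted difference with 95% CI in the original units, for example with robust or bootstrap standard errors. A log(1 + value) scale is less suitable, because with zeros its result depends on the dose unit.
4. Do not adjust for actual length of operation. It is measured after randomisation and could be changed by the surgical field.

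The cost is SAP wording, a few lines of code, and recording the over-3-hour item as planned at screening. With 100 patients the covariates use 4 or 5 degrees of freedom (site 1, stratum 1, duration 1, service 1 or 2), leaving 94 or 93 for error. The service grouping must be settled before unblinding.
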